6.1.2 Baseline Visit

This visit will be performed on Day 1. The following procedures will be performed:

- Randomization: the investigator should randomize the subject through IWRS in which a randomization code and study drug kits will be allocated
- Gynecological examination including evaluation of symptoms and signs of vulvovaginal atrophy other than vaginal dryness
- Recording of adverse events since Screening Visit
- Recording of concomitant medications
- Administration of first dose of study drug by the investigator or by the subject in presence of the investigator Dispensing of dosing instructions and adequate medication supplies for 3 weeks (three medication kits)

6.1.3 Week 3 Visit

This visit will be scheduled on the day after having completed 21 days of treatment. For organizational reasons, a deviation of 3 days before or after the scheduled date is allowed, with the investigator attempting to schedule the visit as close as possible to the estimated ideal date.

The following procedures will be performed:

- Evaluation of symptoms and signs of vaginal atrophy, including vaginal dryness.
- Determination of vaginal pH
- Vaginal smear for evaluation of vaginal cytology
- Recording of adverse events
- Recording of concomitant medications

- Reconciliation of returned medication
- Dispensing adequate medication supplies via IWRS through the Week 8 Visit (two medication kits)

6.1.4 Week 8 Visit

This visit will be scheduled on the day after having completed the end of 8 weeks of study participation. For organizational reasons, a deviation of 5 days before or after the scheduled visit date is allowed, with the investigator attempting to schedule the visit as close as possible to the estimated ideal date.

The following procedures will be performed:

- Recording of adverse events
- Recording of concomitant medications
- Reconciliation of returned medication
- Dispensing adequate medication supplies via IWRS through the Week 12 Visit (two medication kits)

6.1.5 Week 12 Visit/Early Termination Visit

This visit will be scheduled on the day after having completed Week 12 of the study or if the subject terminates study participation before Week 12. For organizational reasons, a deviation of 5 days before or after the estimated ideal date is allowed, with the investigator attempting to schedule the visit as close as possible to the estimated ideal date.

If a subject is discontinued/withdrawn the investigator should register the subject status as such in IWRS.

The following procedures will be performed:

- Evaluation of symptoms and signs of vaginal atrophy, including vaginal dryness
- Determination of vaginal pH
- Vaginal smear for evaluation of vaginal cytology
- Evaluation of global efficacy
- Evaluation of acceptability
- Transvaginal ultrasound in women with a uterus

- Perform an endometrial biopsy in women with a uterus
- Safety laboratory parameters (biochemistry and hematology, including coagulation and lipids, urinalysis) and serum hormone levels. These analyses should be performed under fasting conditions.
- Recording of adverse events
- Measurement of vital signs (blood pressure, heart rate, weight)
- Perform physical examination
- Perform 12-lead electrocardiogram. Two ECG exams will be performed, approximately 5 minutes apart one from the other.
- Perform gynecological examination including a visual inspection of the external genitalia, speculum examination of the vagina and cervix, bimanual palpation of the uterus and ovaries (if present), and breast palpation.
- Recording of concomitant medications
- Reconciliation of returned medication

6.1.6 Week 16 – End-of-Study Phone Call

All subjects who completed the full 12 weeks of study drug will have a phone call scheduled for 4 weeks after last medication dose to record any AEs that may have appeared after treatment discontinuation, and to document changes in concomitant medication use. For organizational reasons, a deviation of 5 days before or after the estimated date will be allowed.

When a subject has completed the study the investigator should register the subject completed in IWRS.

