3.1 Study Design

This study is a double-blind, randomized, dose-ranging, placebo-controlled multicenter study with four parallel groups. Approximately 25 sites in Europe will be included in the study. The study setting will include academic hospitals and gynecological clinics. The study population is postmenopausal women who report moderate to severe vaginal dryness as their most bothersome symptom in addition to other symptoms and/or signs of postmenopausal vulvovaginal atrophy.

After providing informed consent, potential subjects will be evaluated during the screening period to determine if they are eligible to participate in the study. A screening identification number will be assigned to each eligible subject according to their order of arrival into the study at screening visit. Subjects who meet all of the inclusion criteria (see Section 4.1.1) and none of the exclusion criteria (see Section 4.1.2) will be randomized into the study. A total of 280 subjects will be enrolled and randomly allocated to one of the four treatment groups (0.005%, 0.002%, or 0.0008% estriol vaginal gel or placebo vaginal gel); the allocation to treatment group will be 1:1:1:1. A blocked randomization across the entire study (i.e. all sites as a whole) will be used. Subjects will be assigned a randomization code according to their order of arrival into the study at the Baseline Visit. Initial treatment consists of daily vaginal administration of 1 gram of randomly-assigned estriol gel or placebo gel using the supplied applicator. After 21 days of daily administration, treatment will continue with twice-weekly administration up to Week 12 (i.e., Mondays and Thursdays).

The duration of trial participation for each woman is expected to be approximately 20 weeks (from Screening to End-of-Study phone call) although the time on study drug will be approximately 12 weeks. Subject completion is defined as the completion of all phases of the study, including the End-of-Study phone call to be performed for safety purposes at Week 16.

An overview of the study visit procedures is given in the Schedule of Events (Table 1). Details of specific procedures and testing are provided in Section 6.

Table 1: Schedule of Events

Procedure	Screening Visit	Baseline	Week 3	Week 8	Week 12/ Early Termination	Week 16/ End of Study Phone Call
Visit Window (days)	-30 to -1	1	21 ±3	56 ± 5	84 ± 5	112 ± 5
Informed consent	X					
Randomization		X				

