e	Laboratory testing performed under fasting conditions at Screening and Week 12 includes: standard hematology panel plus prothrombin time, activated thromboplastin partial time, fibrinogen, antithrombin III/protein C/protein S; standard chemistry panel (glucose, cholesterol, high-density lipoprotein, low-density lipoprotein, triglycerides albumin, alanine aminotransferase, aspartate aminotransferase, creatine phosphokinase, bilirubin, creatinine, total protein, uric acid, blood urea nitrogen); hormones (estradiol, estriol, estrone, follicle-stimulating hormone, luteinizing hormone); and standard urinalysis with microbiology. Factor V Leiden testing will be performed only at screening visit (or Week 12/ET visit if not obtained at screening)					
f	AEs and SAEs will be recorded from screening (post ICF signature) and subsequently at every study visit and up to 30 days post last study drug administration. Tolerability of study drug will be evaluated at weeks 3, 8, 12, and 16.					
g	For the evaluation of symptoms and signs, each symptom and each sign will be graded as: 0=absent; 1=mild; 2=moderate; 3=severe					
h	Signs and symptoms other than vaginal dryness to be evaluated are the following: Symptoms: dyspareunia, pruritus or itching, burning, dysuria. Signs: pallor, friability, thinning or flattening of folds, presence of petechiae, and dry mucosa					
i	Global efficacy will be assessed as: highly efficacious, efficacious, non-efficacious, detrimental					
j	Global acceptability will be assessed as: excellent, good, acceptable, unacceptable					
k	The investigator will administer the first study medication or will supervise the patient doing the administration					
l	Medication kits will be dispensed via IWRS					

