4.2 Withdrawal of Subjects from the Study

The duration of the study is defined for each subject as the date signed written informed consent is provided through the last follow-up phone call at Week 16.

Participation in this study is strictly voluntary. A subject has the right to withdraw from the study at any time and for any reason. If she chooses to withdraw, the investigator must be informed immediately.

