4.2.2 Handling of Withdrawals

Subjects are free to withdraw from the study or study drug at any time upon request. Subject participation in the study may be stopped at any time at the discretion of the investigator or at the request of the Sponsor.

Subjects who discontinue study drug or active participation in the study will no longer receive study drug. When a subject withdraws from the study, the reason(s) for withdrawal shall be recorded by the investigator on the relevant page of the electronic case report form (eCRF).

Any subject who prematurely terminates participation and who has received at least one dose of the test or reference product will undergo a final examination (see Section 6.1.5 for details).

If study participation is terminated due to an AE possibly related to the study drug or study examinations, the subject must be followed-up by additional examinations according to the medical judgment of the investigator until the abnormal condition is resolved or the investigator deems further observations or examinations to be no longer medically indicated. Subjects who fail to return for final assessments will be contacted by the site (via two telephone calls and then a registered letter) in an attempt to have them comply with the protocol.

It is vital to obtain follow-up data on any subject withdrawn because of an AE or serious AE (SAE). In every case, efforts must be made to undertake protocol-specified, safety, follow-up procedures. All subjects withdrawn from the study should be registered accordingly on the Interactive Web Response System (IWRS).

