6.3.4.2 Eliciting and Documenting Adverse Events

Adverse events will be assessed from the time the subject signs the informed consent form until exit from the study.

Events that occur prior to signing the informed consent form will be entered as medical history; AEs that have an onset after signing the informed consent will be entered on the AE form.

Subjects will be questioned and observed for evidence of AEs, whether or not related to study drug. For any pre-existing condition or abnormal laboratory finding that changes in severity after dosing, the change should be recorded as an AE. New abnormal laboratory findings that are considered clinically significant by the investigator are considered AEs.

All AEs will be collected through the Follow-up Visit (i.e. the Week 16 phone call, 4 weeks after discontinuation of study drug). Adverse event details are to be documented, including start and stop dates, whether continuous or intermittent, severity, any intervention utilized to correct the event, outcome of the event, and the relationship to the study drug.

All AEs determined by the investigator to be related to study drug must be followed until resolution, until they are considered stable, or for at least 30 days after discontinuation of study drug, whichever occurs first.

Adverse events should be classified following the Medical Dictionary for Regulatory Activities (MedDRA). Safety/PV will use the MedDRA medical dictionary to map the AE/SAE verbatim terms to specific system organ classes (SOC) and preferred terms.

Note that, for the purpose of this protocol, the following circumstances (with or without associated adverse event/reaction) should be included in the data base and will be submitted to the Sponsor, being managed in the same way and time as adverse events/reactions: any overdose (with or without associated AEs), abuse, misuse, off-label use, or medication error.

The causal relation between the investigational product and the AE will be assessed by the investigator using the following assessment criteria:

UNRELATED: This category applies to those AEs that are clearly and incontrovertibly due to extraneous causes (disease, environment, etc).

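### The only planned contact after the Week 12/Early Termination visit is for women who complete 12 weeks of drug, while post-treatment adverse events are to be recorded for everyone

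*Protocol*

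**What the plan says.** **Who is called.** Protocol 6.1.6: "All subjects who completed the full 12 weeks of study drug will have a phone call scheduled for 4 weeks after last medication dose", within ± 5 days, to record adverse events and changes in concomitant medication. SAP 4.1.6 repeats the restriction to completers. Protocol 3.1 defines subject completion as "including the End-of-Study phone call to be performed for safety purposes at Week 16" along with all other phases, so the call has a stated safety purpose.

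**What is to be recorded.** Note f to Table 1 (Protocol 3.1) has adverse events and serious adverse events recorded from screening and "subsequently at every study visit and up to 30 days post last study drug administration"; the SAP's Table 1 has a matching note. Protocol 6.3.4.2 adds: "All AEs will be collected through the Follow-up Visit (i.e. the Week 16 phone call, 4 weeks after discontinuation of study drug". Protocol 5.9 and SAP 6.2.5 record concomitant medication to 30 days (± 5) after last dose. None of these is limited to completers. Protocol 4.2 gives the duration of the study as "defined for each subject as the date signed written informed consent is provided through the last follow-up phone call at Week 16".

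**What an early terminator gets.** Under Protocol 4.2.2, a woman who ends participation prematurely and "who has received at least one dose of the test or reference product will undergo a final examination", which is the visit in Protocol 6.1.5. Table 1 in both documents shows nothing between that visit and the Week 16 call.

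**The concern.** The scheduling sentence is narrower than the recording duty it serves. A completer is asked, about four weeks after her last dose, whether anything new has happened. A woman who stops early is seen once and is not asked again, although the same 30-day period applies to her.

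Protocol 6.3.4.2 adds an ambiguity: "Adverse events will be assessed from the time the subject signs the informed consent form until exit from the study". For an early terminator a site could read exit as the Early Termination visit, which cuts short the 30 days in note f. Another site could read Protocol 4.2 and keep following her. Practice could then differ between sites.

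Two things are at stake. One is safety follow-up of women who have stopped an investigational estrogen. The other is comparability within the adverse event tables, because both kinds of women sit in the same Safety population denominator.

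**Working it through.** **1. The provisions side by side**

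| Provision | Covers | Runs to |
|---|---|---|
| Phone call: Protocol 6.1.6, SAP 4.1.6 | Completers of 12 weeks of drug | 4 weeks ± 5 days after last dose |
| Adverse event recording: Table 1 note f and SAP counterpart | No completer limit | 30 days after last dose |
| Adverse event collection: Protocol 6.3.4.2 | All adverse events | The Week 16 call, equated with 4 weeks after stopping drug |
| Concomitant medication: Protocol 5.9, SAP 6.2.5 | No completer limit | 30 ± 5 days after last dose |
| Study duration: Protocol 4.2 | Each subject | The Week 16 call |

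For a completer, the first row supplies the data that the other rows require. For an early terminator, no row supplies a contact after the final examination. The Week 16 column of Table 1 does not settle the matter. It gives day 112 ± 5, which is not tied to an early terminator's last dose, and the section describing the call restricts it to completers.

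**2. How many women**

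Inputs from Protocol 7.5 and SAP 6.1.4: 57 evaluable per group, 18% drop-out, about 70 per group, 280 in total.

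- Plan's own figure: 57 / (1 − 0.18) = 69.5, rounded up to 70 per group. It reproduces.
- Expected drop-outs: 0.18 × 280 = 50.4 women, or 0.18 × 70 = 12.6 per arm.

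This takes the drop-out allowance as the share not completing 12 weeks of drug; the documents give no other figure. It is not a limit. Actual discontinuation may be higher or lower, and the group includes women withdrawn for an adverse event (already followed for that event) and women who may be lost or refuse contact.

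**3. Timing of the completers' call**

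28 − 5 = 23 and 28 + 5 = 33, so the call falls 23 to 33 days after last dose. A call on days 23 to 29 precedes the end of the 30-day window in note f. The same schedule therefore leaves a small shortfall even for completers.

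**4. Route into the tables**

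- Protocol 7.8.4 and the opening of SAP 6.4.1 base the safety assessment on adverse events during the 12 weeks on treatment.
- The classification rules in SAP 6.4.1 make an event treatment-emergent if its onset is later than the first dose. No end date is given.
- The tables report percentages in the Safety population, which is every randomized woman who used at least one dose.

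The first two statements are in tension. Under the classification rule as written, an event with onset in week 14 that a completer mentions at her call is counted. The same event in an early terminator, at the same interval after last dose, is counted only if it reaches the site another way.

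**The case against.** **Existing cover is real.** For women withdrawn because of an adverse event, Protocol 4.2.2 is emphatic: "It is vital to obtain follow-up data on any subject withdrawn because of an AE or serious AE (SAE"). Protocol 6.3.4.1 tells women to contact the investigator if symptoms develop, requires serious events during the study to be reported within 24 hours, and extends reporting to related serious events more than 4 weeks after stopping. Protocol 6.3.4.3 and 6.3.4.6 follow known events to resolution or stability. All of this stands, and it confines the gap to actively asking about new events after the Early Termination visit. It does not close the gap. Following a known event is not asking about a new one, and the two calls and registered letter in Protocol 4.2.2 are for women who miss final assessments.

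**The broader clauses already point the right way.** Protocol 4.2 and 6.3.4.2 can be read as requiring follow-up of everyone, which makes 6.1.6 a drafting slip. That is a fair reading and a reason to treat this as a clarification. Still, the call is booked from the scheduling section.

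**Safety is stated to rest on the 12 weeks of treatment.** This also stands, and it limits the consequence. It does not remove it while the treatment-emergent rule is open-ended.

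**Stronger readings the documents do not support.**
- A reader might infer a definite bias in adverse event rates between arms. That needs a rate of events only a call would elicit and a drop-out difference between arms; the documents give neither.
- A reader might treat all 30 days after last dose as unobserved. Adverse events are recorded at the Early Termination visit, so any days between last dose and that visit are covered.
- A reader might conclude that early terminators are denied biopsy or laboratory results. The call is described for adverse events and medication only, even for completers, and laboratory procedures are left to manuals not seen here. No defect is shown.

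**Conclusion.** The inconsistency is in the current text of both documents and does not depend on any assumed rate. Women who stop early have no scheduled contact after the Early Termination visit, although recording to about 30 days after last dose is required without a completer limit. At the 18% allowance roughly 50 of 280 women, about 12 or 13 per arm, would rely on self-report for new events where completers are asked.

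The effect on treatment-emergent tables is possible under the SAP's rule, but its size and direction cannot be estimated from the documents. Primary efficacy, the gatekeeping procedure and the sample size are unaffected. This is a worthwhile, inexpensive improvement to safety ascertainment. It is not a flaw that threatens the trial's conclusions.

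**What to change.** - In Protocol 6.1.6 and SAP 4.1.6, schedule the call for every woman who has used at least one dose, early terminators included, and time it from last dose by the same rule for everyone.
- Preferably set that rule so the call is not made before day 30, for example 30 to 35 days after last dose. It then covers the whole window in note f and stays within the 30 ± 5 days for concomitant medication.
- Footnote Table 1 in both documents to say that day 112 ± 5 applies to completers. If the day-30 minimum is adopted, move that window to match: for a last dose on day 84, 84 + 30 = 114 and 84 + 35 = 119.

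The cost is a sentence and a footnote in each document and, at the planned allowance, roughly 50 extra phone calls. Clinic visits, blinding and the efficacy analyses do not change. Women who withdraw consent may decline the call, so cover will improve without being complete.

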6.2 Efficacy Assessments

The main efficacy variables in this study are: change in the proportion of superficial and parabasal cells of the vaginal epithelium; change in vaginal pH; and change in the severity of vaginal dryness.

Secondary efficacy variables are: change in the severity of individual vaginal symptoms and signs of vaginal atrophy (other than vaginal dryness); and change in the Global Symptom Score.

The exploratory efficacy variables include evaluation of the final subjective global perception of efficacy by subjects at the end of study and evaluation of acceptability of the therapy at Week 12.

The minimally effective dose of estriol vaginal gel will be determined based on using the gatekeeping procedure outlined in Section 7.8.1.1, the minimal effective dose will therefore be the lowest dose at which a significant difference is seen when compared with placebo.

The gynecological procedures and evaluations to be performed for the assessment of the efficacy variables include the vaginal cytology, determination of the vaginal pH, evaluation of the different vaginal signs and symptoms, determination of the Global Symptom Score, and the evaluation of the global impression of efficacy.

6.2.1. Vaginal Cytology

Vaginal smears will be performed to evaluate the maturation index of the vaginal mucosa at Screening Visit and at the Week 3 and Week 12/Early Termination visits.

Two vaginal smears should be collected per subject, from the bottom of the right and left vaginal walls respectively. The vaginal cytological samples will be fixed whilst they are still moist with a water-soluble fixation spray for cytodiagnosis.

The vaginal cytological samples will be sent to the centralized laboratory for analysis. One sample is to be sent to the central laboratory for analysis, with the second sample retained at the site with no requirement of specific environmental storage conditions. Samples will be evaluated by two different cytopathologists who will be blinded as to subject treatment assignment. The back-up sample will be evaluated only in the event that the initial samples are invalid or have suffered any type of incident such as breakage or loss.

For the cytologic evaluation, the number of parabasal, intermediate, and superficial cells will be calculated. The percentages of each type of cells will be calculated.

